6.1.2 Medtronic Research App

Medtronic's research app (or "study app") will be used for Define AFib to collect iPhone® data (including the iPhone® Health App data, anonymized location services, and EHR/claims data if available), to electronically consent the subject in the app, administer patient questionnaires and to display select data from their LINQ ICM device directly to the patient. This app is not intended as a substitute for medical diagnosis or treatment. This app was developed by Medtronic using the Apple ResearchKit and will be used for other studies in the future. The research app will be available for download in Apple's App Store. The name for this app is the Medtronic Discovery App however, may be renamed through the course of the study. All data collected from Medtronic's research app will be stored in a Medtronic

Page 20 of 48

secure, 21 CFR Part 11 compliant databases with controlled access. The databases have been reviewed and approved by Medtronic's Global Security and Privacy Office.

6.1.3 Data Collection from LINQ Devices

The following (but not limited to) data will be collected passively through the CareLink database. All device parameters and alerts will be programmed by the physician per standard care, and no changes will be mandated for the patient to participate in the study. Data will be collected on an ongoing basis following documented patient consent, and until study termination or patient withdrawal. Select variables will be collected.

- AF Episode
- AF events reported
- Daily Activity Level
- HR Variability

- AF Episode Duration
- Daily AF Burden
- History of EGMs
- HR in AT/AF

- Number of AF Episodes
 Baseline Heart Rate
- Counters
- HR Day

Episodes History

HR Night

Data collection schedule is outlined in section 9.

6.2 Manufacturer

The Reveal LINQ and LINQ II ICM systems are manufactured by Medtronic, Inc.

The Medtronic research app was developed by Medtronic, Inc.

The Apple iPhone® is manufactured by Apple, Inc.

6.3 Packaging

Instructions for use of the devices used in this study are provided within their respective manuals. None of the devices used in this study are investigational and therefore are not labeled with study-specific information.

6.4 Intended Population

The Reveal LINQ and LINQ II ICMs are indicated for the following:

- Patients with clinical syndromes or situations at increased risk of cardiac arrhythmias
- Patients who experience transient symptoms such as dizziness, palpitation, syncope, and chest pain that may suggest a cardiac arrhythmia

See Section 8 for a description in inclusion and criteria.

Medtronic's research app is intended for all participants in the DEFINE AFib study.

Version 4.0 (29JUL2022)

Page 21 of 48

6.5 Product Use

The Reveal LINQ and LINQ II ICMs will be used in accordance with approved indications and site-specific standard of care. No investigational products are being used in this study.

The Medtronic's research app will be available for download in Apple's App Store. All data collected from the DEFINE AFib Study research app will be stored in a Medtronic secure, 21 CFR Part 11 compliant databases with controlled access. The databases have been reviewed and approved by Medtronic's Global Security and Privacy Office.

7. Study Site Requirements

Study Site requirements, including site selection and activation, can be found in each specific DEFINE AFib study addendum.

8. Selection of Subjects

Selection of subjects, including study population, subject enrollment and inclusion/exclusion criteria can be found in each specific DEFINE AFib study addendum.

9. Study Procedures

9.1 Schedule of Events

Clinical data are collected at designated time points throughout the study. The requirements for data collection and study procedures by visit are summarized in Table 3 below.

Table 3: Study Procedures Organized by Study Events

STUDY PROCEDURE/ DATA COLLECTION	Enrollment	Daily Data Collection	Patient Surveys	Study Exit
Informed Consent	X			
Inclusion/Exclusion Assessment	X			
Medical History, Demographics	X			
AF-Associated Symptoms			X	
HCU			X	
System Modification			X	
Change in Medical Management for AF			Х	
Quality of Life Questionnaires	Χ		Х	
Study App Use Metrics		Х		
HealthKit Data Including EHR,if available		Х		
Patient Impact			Х	

Table 4: Survey Type and Deployment Logic

Survey Category	• Survey	• Survey Type	Deployment Prerequisites	Rules	Expiration
Medical History	Patient history	Static	eConsent completed	Only completed once at joining of study, necessary for enrollment	No expiration
	 Medication history (MDT developed tool) 	Static	eConsent completed	Completed at beginning of study, available to update/modify over study timeline	No expiration
Quality of Life	• EQ-5D-5L	Static	eConsent completed	Starting at enrollment and then every 3 months (every 90 days +/-2 days**)	30 days post issuance
	• AFEQT	Static	eConsent completed	Starting at enrollment and then monthly (every 30 days +/- 2 days**)	14 days post issuance
Healthcare Utilization	• HCU	Dynamic	Starting 30 days after enrollment	Starting 30 days after enrollment and then monthly (30 days +/-5	7 days post- issuance

Version 4.0 (29JUL2022)

Page 23 of 48

			or first triggered event	days*) (+/-2days**) (For triggered surveys, including healthcare facility geofence and daily AF burden from CareLink see section 9.9.2) HCU survey should always be deployed with Symptom and Symptom Severity Survey	
Symptom and Symptom Severity	MAFSI and modified EHRA symptom severity	• Dynamic	Starting 30 days after enrollment or first triggered event	Starting 30 days after enrollment and then monthly (30 days +/- 5 day*)(+/-2days**) (For triggered surveys, including healthcare facility geofence and daily AF burden from CareLink see section 9.9.2) Symptom and Symptom Severity survey should always be deployed with HCU survey	7 days post issuance
Medication	• SMAQ	• Static	• Starting 90 days after enrollment (+/-2 days**)	Starting 90 days after enrollment and then every 3 months (every 90 days +/-2days**)	30 days post- issuance
• Patient App	• Patient impact	• Static	 Starting 6 months after enrollment (180 days +/- 2 days**), 	Starting 6 months after enrollment and then every 6 months (every 180 days +/-2 days**)	90 days post- issuance

^{*+/-5} days survey administered randomly within each deployment window

9.2 Subject Screening

Interested patients will be required to download Medtronic's research application. Upon first accessing the application after downloading, potential subjects will undergo authentication. Potential participants will complete the eligibility survey available in the app. Patients who meet the inclusion criteria based on self-report and a device serial number check via the app will be invited to participate in the study and directed to a digital consent form within the app for their review and electronic signature. A phone number for the Help Desk will be provided prior to consenting of the subject if the subject has any questions regarding their participation in the clinical study.

^{**+/-2} days is to correct for survey transmission issues

Version 4.0 (29JUL2022)

Page 24 of 48

9.3 Prior and Concomitant Medications/Therapies

There are no requirements or restrictions with respect to prior or concomitant medications. Patients will be asked to record the medications they are taking and will be routinely asked to recall medication compliance through regularly deployed surveys throughout the study.

9.4 Subject Consent and Enrollment

The informed consent is defined as a legally effective documented confirmation of a patient's voluntary agreement to participate in a particular clinical study after information has been given to the patient through the study app on all aspects of the clinical study that are relevant to the patient's decision to participate. This process includes obtaining an ICF and an Authorization to Use and Disclose Personal Health Information that has been approved by an Institutional Review Board and electronically signed and dated by the patient.

Prior to enrolling patients, approval of the CIP, ICF, and all other written study information to be provided to the patients must have been approved by a registered IRB. The document(s) must be controlled (i.e. versioned and dated) to ensure it is clear which version(s) were approved.

The investigator must notify patients of any significant new findings about the study that become available during the study which are pertinent to the safety and well-being of the patient, as this could impact a patient's willingness to participate in the study. If relevant, approval may be requested from patients to confirm their continued participation.

Electronic consent will be obtained prior to subject enrollment and before any study-specific procedures are initiated. Consent will be self-administered by the patient via the informed consent process. The process of obtaining informed consent must be conducted without using coercion or undue improper influence on or inducement of the patient to participate by the study or affiliated personnel. The informed consent process shall not waive or appear to waive patient's legal rights. The language used shall be as non-technical as possible and must be understandable to the patient.

The patient must have ample time and opportunity to read and understand the ICF, to inquire about details of the study via the study help desk, and to decide whether to participate in the clinical study. All questions about the study should be answered to the satisfaction of the patient. To facilitate patient access for questions, patients will have access to the study help desk, which will be equipped to answer study-related questions. A phone number for the Help Desk will be provided prior to consenting of the subject to allow the subject the ability to answer any questions regarding their participation in the clinical study.

When the patient decides to participate in the clinical study, the ICF must be electronically signed and dated by the subject acknowledging that their participation is voluntary.

Version 4.0 (29JUL2022)

Page 25 of 48

The ICF and Authorization to Use and Disclose Personal Health Information will be electronic. A copy of the signed and dated ICF and Authorization documents will be available within Medtronic's research app for patient reference. An additional copy of the signed and dated ICF and Authorization will be stored in a secure part 11 compliant system, access-controlled Medtronic database and shared with the primary investigator upon request.

The informed consent will be obtained the same day the subject is eligible to begin participating in study-related procedures, and therefore consent date and time will be documented in the meta-data collected with consent. The study app will allow for the patient to access their consent at any time.

9.5 Randomization and Treatment Assignment

There will be no randomization or treatment assignments as this is an observational study.

9.6 Medication Use and Compliance

Patients will be asked to log medications at baseline and asked at regular intervals to update their medication list if there are any changes throughout the duration of their participation in the DEFINE AFib study (Table 4). Patients will store current medications in their research profile and update every 6 months; medication use and compliance assessed via the SMAQ survey deployed every 3 months. For patients with health record access, statistical models will be developed to estimate the proportion of days covered by leveraging EHR or claims data and/or patient surveys regarding prescription fills and/or refills. All changes in medication use will be marked with time and date via meta-data tracked in Medtronic's research application. All medication changes will be confirmed.

9.7 Survey and Device Data Non-Compliance

Monthly reports will be generated to assess response rates on surveys. Patients with missing survey responses or other incomplete tasks will be sent reminders through the app, via email, and via text depending on which communication methods are available and the patient has enabled. A schedule of these reminders can be found in Table 5. In the instance that a patient has undergone a prolonged period of time without transmitting device data, they will be notified via the app. At 90 days, mortality, HCUs, and specific clinical outcome status will be assessed via EHR or confirmed via study site personnel. After 90 days, if confirmed to be alive, they will continue to be monitored but may be excluded from statistical analysis.

Subjects will be reimbursed \$25 every 6 months if they complete >75% of surveys. Subjects will receive an electronic gift card to their email.

Table 5: Notification and Reminder Schedule

Expiration Schedule	Reminder Schedule
7 Day Expiration Schedule	4 Days post issuance
14 Day Expiration Schedule	7 Days post issuance

Version 4.0 (29JUL2022)

Page 26 of 48

1 Month Expiration Schedule	10 Days post issuance, then 20 days post issuance if action not completed
3 Month Expiration Schedule	10 Days post issuance, then 20 days post issuance if action not completed
6 Month Expiration Schedule	10 Days post issuance, then 20 days post issuance if action not completed

9.8 Assessment of Safety

Because 1) this is an observational study using market approved devices for approved indications and 2) there are no study aims evaluating device safety, adverse events will not be collected. Should any new risks associated with the study be identified including patient data security, patients will be notified via push notifications, in-app messaging, email, and SMS text message, depending on what form of communications the patient has opted into. Physicians will be notified of any new risks associated with the study. Continuous monitoring of study risks will be performed using Medtronic's Global Security Office-required security controls which include monitoring procedures/platforms that are capable of logging, monitoring, detecting data breaches and app problems. These procedures are governed by Medtronic' Global Security Office and Cloud Governance teams. Monitoring of study risks will be performed using standard monitoring procedures.

9.9 Recording Data

The following data will be collected passively through Medtronic's research app. Data will be collected on an ongoing basis following documented patient consent, and until study termination or patient withdrawal. Following consent, patients will create a profile, opt in to sharing location, EHR data and other optional components of the study and the patient will have the opportunity to change data permissions that determine collectable data throughout the study. If patients consent to sharing their EHR data, that patient's EHR data will be pulled via the Apple Health app. If EHR access is available, it will be used to confirm patient-reported events as described in section 12. EHR data may also be used to compile and analyze variables as outlined in section 13.

- Electronic Health Records
 - Clinical Vitals
 - Diagnoses/Conditions
 - Lab results
 - Medications
 - Medical procedures/clinical actions
 - Patient mortality

- Health app data (when available, including but not limited to)
 - Step counts to assess activity
 - Nutrition
 - Sleep
 - Vitals
 - Glucose
 - Blood pressure
 - SPO₂
 - Body measurements:
 - Weight
 - Height
 - Body mass index
- Location services (when available)
 - Anonymized geofencing triggers

9.9.1 Geofencing and Location Services

Use of geofences will only be permissible in patients who have consented and enabled to the use of their phone's location services feature. Geofenced facilities will include 12,000+ hospitals and urgent care healthcare facilities in which a patient is likely to seek care. Only anonymized geofence data will be collected which cannot be connected back to the patient it originated from. After Consent, Medtronic servers will deploy the appropriate surveys under the logic provided in Table 4.

9.9.2 Patient Surveys

Patient surveys will be administered to assess medical history, QoL, HCU, changes in medical management, AF-associated symptoms, and medication use. Surveys will also be administered to evaluate patient preferences for viewing and interacting with device data. Exact content of the surveys may change throughout the study, but any significant content changes will be submitted to IRBs for approval.

Survey deployment logic is outlined in Table 4.

Version 4.0 (29JUL2022) Page 28 of 48 Medtronic

QoL Questionnaires

- The EQ-5D-5L general QoL survey will be distributed via the app at enrollment and then every 3 months(90 days +/-2 days) to assess general quality of life metrics
- AFEQT, an AF specific QoL survey will be deployed via the app at enrollment and then every month (30 days +/-2 days) to characterize and assess the impact of AF on each patient

• Symptom Survey:

- A symptom survey will be administered to characterize the presence and severity of AFrelated symptoms when a patient crosses a predefined healthcare facility geofence, reaches the threshold for a single AF episode or daily AF burden or AF pattern, or;
- On a routine monthly (30 days +/-5 days) schedule unless a symptom survey has been deployed for any reason within the previous 7 days.

Healthcare Survey

- A healthcare survey will be deployed to characterize healthcare utilization and modifications to patient care (administration of medical interventions/procedures) when a patient crosses a predefined healthcare facility geofence, reaches the threshold for a single AF episode or daily AF burden or AF pattern, or;
- On a routine monthly (30 days +/-5 days) schedule unless a symptom survey has been deployed for any reason within the previous 7 days.

Medication compliance

Patients will answer the Simplified Medication Adherence Questionnaire (SMAQ) every
 3 months (90 days +/- 2 days) following initial enrollment.

Medication list

 Patients will be prompted to input/update their medications upon enrolling in the study and every 6 months (180 days +/-2 days) following initial enrollment.

Surveys will also be administered to evaluate patient preferences for viewing and interacting with device data. Data around app-use will also be collected (time in app, app feature use, number of clicks, etc.).

Version 4.0 (29JUL2022)

Page 29 of 48

In the event that the patient has lost connectivity (no signal or phone powered off) for an extended period of time, all non-expired surveys will be received upon first opportunity of connectivity. Expiration windows will remain consistent as noted in table 4 regardless of connectivity.

9.9.2.1 Dynamic Surveys

The HCU and Symptom survey are dynamic in nature. Patients will be prompted to complete surveys through Medtronic's research app. Surveys will be triggered at variable times based on the following factors:

- Time from enrollment
- Time since last survey (HCU and Symptom and Symptom Severity surveys)
- ICM device data (triggers HCU and Symptom and Symptom Severity surveys)
 - o A single AF episode lasting longer than 1-hour
 - Cumulative daily AF burden of 5% or greater
 - A patient meets the running average/AF pattern threshold as developed by a prior internal analysis
- Geofence (triggers HCU and symptom surveys)
 - Patient crosses a geofence threshold and remains within the geofenced area for ≥45 minutes

Each patient will receive surveys via one of three methods: 1) Regularly scheduled surveys at specified cadences, 2) AF burden or pattern trigger detected via the Reveal LINQ or LINQ II device (or future market-released LINQ devices) and transmitted through CareLink, 3) a patient crossing and staying within a geofence. Each regularly scheduled deployment window will be +/- 5 days around 30 days from previous survey deployment, with the survey administered randomly within each deployment window. This method reduces the likelihood that a patient will suspect a survey has been given in response to an AF episode they experienced, and helps to avoid any bias associated with the expectation of a survey at a particular cadence. Additionally, patients may receive a HCU and symptom survey at pre-specified trigger points based on Reveal LINQ or LINQ II (or future market-released LINQ devices) detected AF burden or AF patterns, or via the patient being present in a geofenced healthcare facility, within 24-48 hours of the trigger being activated in order to best associate AF patterns with patient health and environmental factors. Patients who trigger any of the AF burden thresholds for HCU or symptom survey deployment will, at the first instance, all receive the assigned surveys. Patients will not be notified which method triggered a survey. Thereafter, any AF burden trigger will be administered at a rate of 50%,

Version 4.0 (29JUL2022)

Page 30 of 48

allowing for the testing of bias introduced by triggered survey deployment and reduce patient survey burden.

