13.3.1 Hypothesis

No formal statistical hypotheses will be tested for this objective. Rather, the goal will be to determine whether a risk prediction model can be developed from device-collected measurements that can has adequate sensitivity and specificity to be of use in a clinical setting.

Analysis Methods

Various risk prediction models will be developed and compared to each other. The model(s) with best predictive power will be selected. The input data of these models might be composed of values (original or derived) collected by LINQ ICMs, and the output of the model will be the risk of patient having a AF-related HCU in the future. The model may also account for attributes of patients' medical histories, including CHA2DS2-VASc scores, individual components of CHA2DS2-VASc scores and any other medical

Page 36 of 48

[figure not shown]

history information provided by the patient at enrollment. The predictive value of the model will generally be assessed against the predictive power of any clinical tools available at the time of model development. If additional predictive tools become available at the time of model development, those tools can be integrated into the development of the model and the value of the model will reflect the incremental benefit provided above and beyond the available clinical tools.

Endpoint: Confirmed healthcare visit in the inpatient hospital, outpatient hospital, clinic/office, emergency department, or other care location (including remote visits) where AF was the reason or suspected reason for healthcare interaction.

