5.1 Healthcare Utilization Confirmation

Healthcare utilization and modification to treatment or management of AF will be reviewed and confirmed via EHR by healthcare site personnel for subjects with available health records to compare to patient completed surveys. Trained and Delegated personnel will be sent patient reported outcomes via a part 11 compliant system for only the subjects that are part of their care network or clinic and asked to confirm patient HCU reports. There will be a standardized set of questions related to each HCU and/or medication/treatment change that includes whether or not the patient-reported utilization/change truly occurred. The reason and specific details for each visit will be recorded (as determined by the treating clinician in the EHR). If there are errors in the patient report, the designated site personnel will have the opportunity to record a correction stating the true events that happened upon a patient's visit to their affiliated health care facility. This process will also be used for all exits performed by the sponsor, as outlined in section 9 of the DEFINE AFib Core CIP v3.0. Site personnel will be asked to determine patient's mortality status along with any HCUs or medication/treatment changes/certain clinical outcomes since the last reported event. Non-confirmable events will be noted as such and will not contribute to the study's endpoints.

Table 7 Healthcare Utilization Definitions

Healthcare Utilizations (HCU)	All inpatient hospitalizations, outpatient hospital encounters, emergency
	department visits, clinic visits, urgent care visits, rehab center or other care location
Otilizations (HCO)	interactions (including remote visits)

Version: 2.0 29JUL2022 Page 12 of 17

CV-related HCU	A healthcare utilization relating to the heart and the blood vessels or the circulation (e.g., atrial fibrillation, myocardial infarction, stroke, peripheral vascular disease, heart failure).
AF-related HCU	HCU related to AF, suspected AF, AF treatment, or complications related to AF (including bleeding and drug toxicity as determined by treating clinician.
HF-related HCU	A healthcare utilization related to worsening heart failure signs and symptoms (as determined by treating clinicians) such as (but not limited to) hypervolemic and hypovolemic status requiring the administration, alteration, adjustment, or augmentation of HF therapy (diuretics, inotropes and/or vasodilators etc.) or the utilization of ultrafiltration devices.

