4.1 Primary Objective

To evaluate whether summary and episodic measurements collected by market-released LINQ ICMs are able to predict increased AF-related healthcare utilization (HCU)

Endpoint: Confirmed healthcare visit in the inpatient hospital, outpatient hospital, clinic/office, emergency department, or other care location (including remote visits) where AF was a reason or suspected reason for healthcare interaction

[figure not shown]
Investigation Plan 5.

DEFINE AFib is an observational, post-market clinical study intended to leverage machine learning to evaluate the association between complex patterns of device-detected AF and elevated healthcare utilization, reduced QoL and specific clinical outcomes in patients with a LINQ ICM. These data will improve the business understanding of how data from the LINQ ICM can be used to guide the management of patients with AF.

This study is expected to be conducted at approximately 30 centers in the United States, and it will enroll approximately 5,000 patients (see section 13.1 of the CIP). Study subjects will be followed for up to 5 years, until study closure, or until their LINQ ICM either completes its service life or is explanted, upon which time they will no longer be followed. Study closure may occur when Medtronic requirements have been satisfied per the CIP and/or following a decision by Medtronic or applicable external parties (i.e. institutional review board (IRB) or regulatory authority) to discontinue the study.

Revision [2.0]

Page 7 of 25

Enrollment is anticipated to last for up to 3 years. The estimated total study duration is up to 7 years, representing a three-year enrollment period and up to 5 years of follow-up for all patients.

Inclusion Criteria

- Patients with a Reveal LINQ or LINQ II ICM who have a self-reported history of AF and who have received an ICM for the following device logged indications, categorized into the following groups:
 - o **Stroke**: Cryptogenic stroke indication
 - o **AF management**: AF management and post-ablation management indications
 - Suspected AF: Suspected AF and palpitations indications
- Individual access and ability to use an Apple iPhone® compatible with Medtronic's research app (iOS v. 13.X or higher)
- Patient is willing and able to comply with the protocol, including CareLink transmissions (requires
 adequate connectivity), remotely administered instructions, and remote survey participation
- Patient is 22 years of age or older

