After all models have been trained and tuned, all final models (i.e. for each clinical endpoint and prediction modeling strategy) will be fitted to the testing dataset resulting in a prediction of each patient's individual probabilities of having the clinical event in the predictive window (i.e. between t+l and t+l+w). More specifically, all models will generate risk prediction (for the clinical event they were designed to predict) for each patient at each day (starting at the bth). The true binary values and the corresponding prediction risk scores will be used to compute the area under the receiver operating characteristic (AUROC), sensitivity, specificity, negative predictive value (NPV) and positive predictive value (PPV). Bootstrapping will be used to compute 95% CIs for these performance metrics.

For each outcome, the performance of the risk prediction models will be presented in contrast to the performance of comparable clinical practices. However, as a guideline, the following scale might be used to help choose the adjective to refer the performance of each model:

AUROC ≤ 0.5: fail

DEFINE AFib Statistical Analysis Plan Form Medtronic Revision [2.0] Page 17 of 25

0.5 < AUROC ≤ 0.6: poor

0.6 < AUROC ≤ 0.7: fair

[figure not shown]
0.7 < AUROC ≤ 0.8: good

[figure not shown]
0.8 < AUROC ≤ 0.9: great

[figure not shown]
AUROC > 0.9: excellent

[figure not shown]
Determination of Subjects/Data for Analysis

Subjects in the full analysis set who have completed all enrollment surveys will be included in the primary objective analysis. Subject follow up might be limited by lack of device information.

[figure not shown]

[figure not shown]

DEFINE AFib Statistical Analysis Plan Form Medtronic Page 20 of 25 Revision [2.0]

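### LINQ-detected AF, the predictor, also raises how often patients are asked about the endpoint, and the visible primary evaluation in SAP 7.9.1 does not use the 50% deployment rule meant to test that bias

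*Protocol*

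**What the plan says.** **Predictor.** CIP 13.3.1: "The input data of these models might be composed of values (original or derived) collected by LINQ ICMs".

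**Endpoint.** A confirmed visit "where AF was a reason or suspected reason for healthcare interaction" (SAP 4.1).

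**How visits are found.** Everyone gets the HCU survey about every 30 days (within 5 days either way, counted from the previous deployment). CIP 9.9.2.1 adds device triggers: "A single AF episode lasting longer than 1-hour", "Cumulative daily AF burden of 5% or greater", or an AF-pattern threshold. "Patients who trigger any of the AF burden thresholds for HCU or symptom survey deployment will, at the first instance, all receive the assigned surveys"; later AF triggers are deployed at a 50% rate, "allowing for the testing of bias introduced by triggered survey deployment and reduce patient survey burden". CIP section 5 blocks a triggered survey within 7 days of the last one of the same kind. A geofence stay of at least 45 minutes also sends the survey.

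**Confirmation.** Under Site Assisted Addendum 5.1, trained site staff receive the patient-reported outcomes and are "asked to confirm patient HCU reports". Events that cannot be confirmed do not count.

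**Evaluation.** SAP 7.2 accepts monthly surveys, triggered surveys or EHR as HCU information without distinguishing them. SAP 7.9.1 labels each sliding window by whether the event occurred, and then: "The true binary values and the corresponding prediction risk scores will be used to compute the area under the receiver operating characteristic (AUROC"), with sensitivity, specificity, NPV and PPV. The visible text on labels, split strata, sampling, tuning and testing has no term for survey route or for sent/withheld status.

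**The concern.** The quantity being tested as a predictor also controls how often the outcome is looked for. If surveys are missed or visits forgotten, a patient whose LINQ keeps triggering has more chances to report a given visit than a patient whose LINQ is quiet. Recorded labels then favour high-AF windows even if AF and visits are unrelated.

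The planned safeguards cannot show this. The held-out test set, the bootstrap intervals and the error analysis by cohort (SAP 7.3) all use the same labels. The comparison with existing clinical tools is also affected: a score such as CHA2DS2-VASc sends no surveys, so the bias would tend to enlarge the apparent gain from LINQ data. The CIP anticipated the problem and built in a contrast. At stake is whether that contrast is used where the primary result is produced.

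**Working it through.** **1. The plan's event count and its sampling error.** 0.21 × 5,000 = 1,050 AF-related events; halved for incomplete data, 525, as stated. The 20% test set holds 0.20 × 525 = 105. Treating these as independent, with 10,000 event-free windows (assumption), the Hanley-McNeil 95% half-width is about 0.056 at AUROC 0.7.

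**2. Survey frequency.** Simulating the stated rules (30 ± 5 days from last deployment, 7-day block, AF triggers sent at 50%):

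| AF trigger days | HCU surveys per patient-year |
|---|---|
| none | 12.1 |
| 1 in 30 | 13.9 |
| 1 in 7 | 19.6 |
| every day | 40.7 |

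Daily triggering gives 40.7/12.1 = 3.4 times as many surveys, even with the 50% rule.

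**3. Capture of a true visit.** A visit counts as captured if a completed survey is issued within the recall period. Completion and recall are assumptions; the documents give neither. With 30-day recall:

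| Completion | No triggers | Daily triggers | Ratio R |
|---|---|---|---|
| 50% | 48% | 88% | 1.83 |
| 60% | 59% | 94% | 1.60 |
| 75% | 70% | 99% | 1.42 |
| 90% | 86% | 100% | 1.16 |

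Separate runs differ by a few points; the 59% cell came out between 58% and 61%.

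**4. Effect on AUROC.** For a binary high-AF marker covering a share f of windows, AUROC = 0.5 + (TPR − f)/2, with TPR = fRk/(fRk + 1 − f), where k is the true rate ratio. Take f = 0.3 (assumption).

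- No true effect (k = 1), R = 1.83: TPR = 0.549/1.249 = 0.440, AUROC 0.570. With R = 1.16, 0.516. The correct value is 0.500.
- k = 4: the correct value is 0.5 + (1.2/1.9 − 0.3)/2 = 0.666. The observed value is 0.682 at 90% completion, 0.704 at 75% and 0.729 at 50%. The SAP's fair/good cut is 0.7.
- A wider grid with no true effect (completion 40-80%, recall 30 or 60 days, triggers on 10% or 50% of days, f 0.2-0.4) gives 0.503 to 0.578.

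**5. Where the bias fades.**

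- 60-day recall: R = 1.03 to 1.43, so AUROC 0.503 to 0.540 at f = 0.3 with no true effect.
- Unlimited perfect recall: R = 1.00.
- One isolated trigger: capture of visits 7-37 days later was 60% with and without it. The survey goes out within 24-48 hours, asks mostly about earlier visits, and resets the 30-day clock.
- If geofence surveys caught half of visits (assumption; 60% completion, 30-day recall, triggers on 10% of days), capture moves from 61% vs 72% to 66% vs 74%. R falls from 1.18 to 1.12.

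**6. What the 50% rule can show.** At 60% completion, capture around sent versus withheld triggers was 79% vs 69% with triggers on 10% of days, but 94% vs 92% with triggers on 50% of days, because a sent trigger soon follows a withheld one. Detecting a 1.3-fold difference (two-sided 5%, 80% power) needs about 3,780 occasions per arm at 5.0% vs 6.5%, 9,798 at 2.0% vs 2.6%, and 19,827 at 1.0% vs 1.3%. These rates are assumed, and clustering within patients raises the numbers.

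**7. Two sensitivity analyses that do not work.**

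- Keeping only windows without an AF-triggered survey: about 29% of 30-day windows qualify with triggers on 10% of days and about 0.1% with 50%. This removes nearly all high-AF time, and a single inverse-50% weight is wrong when a window holds several triggers.
- Counting only scheduled-survey events: a scheduled survey at day 30 requires no sent trigger on days 8-29. That has probability 0.95^22 = 0.32 with triggers on 10% of days and 0.75^22 = 0.002 with 50%. High-AF patients get few scheduled surveys, so the bias reverses.

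**The case against.** The strongest case has four parts.

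- **Other routes exist.** Geofence surveys do not depend on LINQ data and fall outside the 50% rule. EHR data may be shared, and sites look for HCUs when the sponsor exits a patient. This stands as a reason for a smaller bias, but not for none. Location and EHR sharing are optional. Geofences cover hospitals and urgent care, while the endpoint includes office and remote visits. Site review without a patient report is described only for sponsor exits and for 90 days without device data.
- **The size rests on assumptions.** This stands. Completion, recall and trigger persistence are not in the documents, and reminders and payment for completing more than 75% of surveys push completion up. A reader might infer that a positive primary result could not be told apart from ascertainment. The documents do not support that: the bias runs from near zero to about the size of the sampling error, and it needs persistent triggering.
- **The 50% rule is not described as randomised.** This stands. A reader might infer a ready-made randomised comparison with a known probability. CIP 9.9.2.1 gives only a rate, with no mechanism or unit; it uses randomness only for the timing of scheduled surveys.
- **The test may be elsewhere.** The CIP version history refers to ancillary objectives, and several SAP pages show no text. The SAP also allows further analyses and revision after the interim analysis. So it cannot be said that the plan has no test of this bias, only that the visible primary evaluation has none.

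**Conclusion.** The concern holds in limited form. LINQ-detected AF raises the frequency of the survey through which most endpoint visits are first reported, so capture can be higher in patients with recurrent triggers. The visible SAP 7.9.1 does not use the rule the CIP set up to test this. Following the plan exactly would leave any such bias in all five primary metrics.

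Under 40-90% completion, 30-60 day recall and persistent triggering, all assumed, a marker with no predictive value would show an AUROC of about 0.50 to 0.58. The upper end matches or slightly exceeds the sampling half-width of about 0.056, and could move a model across the SAP's 0.7 cut. With long recall or isolated triggers the effect is negligible. Because the size is unknown and partial safeguards exist, this is a should-fix: it qualifies the primary result and does not invalidate it.

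**What to change.** Amend SAP 7.9.1, Testing:

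- **(a) Define and log.** State the mechanism and unit of the 50% rule (trigger, day or patient). Record sent/withheld status for every AF trigger, and the route by which each HCU was ascertained.
- **(b) Sent versus withheld.** For second and later AF triggers, report confirmed AF-related HCU in a fixed interval around sent and withheld triggers, with patient-clustered confidence intervals. State that this understates the bias when triggers are frequent, and that first triggers, always sent, give no contrast.
- **(c) Second set of metrics.** Report AUROC, sensitivity, specificity, NPV and PPV again in test-set patients whose HCUs are ascertained from EHR regardless of survey, with a rule for classing such an encounter as AF-related. Qualify the conclusion on LINQ prediction if the two sets differ materially.

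Do not restrict to windows without AF-triggered surveys, and do not count only scheduled-survey events, for the reasons in step 7 of the working.

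**Cost.** SAP text, two analyses and, if not already kept, a log field. The contrast in (b) may be imprecise. The set in (c) is smaller: if half the test events came from EHR-sharing patients (assumption), the half-width would grow to about 0.056 × √2 = 0.079. EHR sharing is also optional, so that subset is selective. These limits should be reported with the results.
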